8.5. Patient Files

The RP and trained staff at the registry sites will maintain files on each enrolled patient. In addition, all original source documentation is expected to be stored at the site for the longest possible time required by local applicable regulations. The RP will be instructed to notify Pfizer before any destruction of medical records of registry participants. If an RP becomes involved in follow-up with other clinicians, the associated documentation provided by other clinicians will be maintained in the patient's registry file at the site.

8.6. Record Retention

To enable evaluations and/or audits from regulatory authorities or Pfizer, the investigator agrees to keep records, including the identity of all participating patients (sufficient information to link records, e.g., CRFs and hospital records), all original signed informed consent forms, copies of all CRFs, serious adverse event forms, source documents, and detailed records of treatment disposition, and adequate documentation of relevant correspondence (e.g., letters, meeting minutes, telephone calls reports). The records should be retained by the investigator according to local regulations, or as specified in the Clinical Study Agreement, whichever is longer.

The RP at each registry site will receive a registry site file (RSF) upon initiation of the Registry. This RSF will contain all documents necessary for the conduct of the registry and will be updated and completed throughout the study. The RSF must be available for review in the event the site is selected for monitoring, audits, or inspections and must be safely archived for at least 5 years after the completion the registry. Documents to be archived include the patient enrolment log and the signed patient ICFs. In the event that archiving of the RSF is no longer possible at the site, the RP will be instructed to notify Pfizer.

The study records must be transferred to a designee acceptable to Pfizer, such as another investigator, another institution, or to an independent third party arranged by Pfizer. The investigator must obtain Pfizer's written permission before disposing of any records, even if retention requirements have been met.

8.7. Quality Assurance, and Inspection by Authorities

The registry database will be housed at the CRO in a physically and logically secure computer system maintained by the CRO in accordance with its written security policy. The system meets approved established standards for the security of health information and is validated. The system also meets the standards of the International Committee on Harmonisation (ICH) guideline E6R1 regarding electronic study data handling and is available for audit upon request. Patient confidentiality will be strictly maintained.

The protocol, each step of the data capture procedure, and the handling of the data, as well as the eventual registry report, is subject to independent clinical quality assurance audits. Audits

may be conducted by the Sponsor, or its designated organization, at any time during or after registry initiation to ensure the validity and integrity of the registry data. In addition, the Registry may be inspected by health authorities.

9. ADVERSE EVENT REPORTING AND SERIOUS ADVERSE EVENT REPORTING

ADVERSE EVENTS

All observed or volunteered adverse events regardless of treatment group (if applicable) or suspected causal relationship to etanercept will be recorded on the adverse event page(s) of the case report form (CRF) as follows.

For all adverse events, the investigator must pursue and obtain information adequate both to determine the outcome of the adverse event and to assess whether it meets the criteria for classification as a serious adverse event (see section "Serious Adverse Events") requiring immediate notification to Pfizer or a Pfizer-designated representative. For all adverse events, sufficient information should be obtained by the investigator to determine the causality of the adverse event. The investigator is required to assess causality. For adverse events with a causal relationship to etanercept, follow-up by the investigator is required until the event or its sequels resolve or stabilize at a level acceptable to the investigator, and Pfizer concurs with that assessment.

All AEs must be evaluated by the site and assessed for seriousness, as defined below in [Section 9.1](#).

REPORTING PERIOD

All reportable serious and non-serious AEs directly observed or reported by the patient or caregiver to the physician or other site personnel, from the time of enrolment (i.e., informed consent has been obtained and the patient has received at least one dose of etanercept) through patient discontinuation from the registry, end of the observation period, or 28 days after the last dose of etanercept, whichever is later, will be assessed and recorded, if applicable, within the CRF. If a patient was administered etanercept on the last day of the observation period, then the reporting period should be extended for 28 calendar days following the end of observation. The site will record the diagnosis, if available. If no diagnosis is available, the site will be instructed to record each sign and symptom as an individual event.

If the investigator becomes aware of a SAE occurring at any time after completion of the study and s/he considers the SAE to be related to etanercept, the SAE also must be reported to Pfizer Safety.

Specific AE data (i.e., serious infections, pre-specified opportunistic infections, and malignancies) will be obtained at scheduled or unscheduled interviews based on information provided spontaneously by the patient (or parent) and/or by thorough questioning of the patient (or parent). To elicit reports of these events, each interview will begin with simple open-ended questions and questions designed to collect information regarding the specific outcomes of interest.

If a patient is seen by a non-RP physician or hospitalised in relation to an AE, the RP or trained registry site personnel should, in a timely manner, make every effort to follow-up with the treating physician or relevant concerned health care provider to obtain all information necessary for the accurate reporting of the event.

For instances where an event is reported by the patient and/or treated by a non-RP, registry staff will contact the treating physician or other health care provider as described and authorized by the informed consent, in order to obtain relevant information necessary for complete reporting of adverse events.

9.1. Definitions

An adverse event (AE) is any untoward medical occurrence in a patient administered a medicinal product; the event need not necessarily have a causal relationship with the treatment or usage. Examples of AEs include but are not limited to:

- Abnormal test findings (see below for circumstances in which an abnormal test finding constitutes an adverse event)
- Clinically significant symptoms and signs
- Changes in physical examination findings
- Hypersensitivity
- Progression/worsening of underlying disease
- Lack of efficacy

- Drug abuse

- Drug dependency

Additionally, they may include the signs or symptoms resulting from:

- Drug overdose
- Drug withdrawal
-

- Drug misuse
- Drug interactions
-
- Extravasation
- Exposure during pregnancy
- Exposure during breast feeding
- Medication error
- Occupational exposure

ABNORMAL TEST FINDINGS

The criteria for determining whether an abnormal objective test finding should be reported as an AE are as follows:

- Test result is associated with accompanying symptoms, and/or
- Test result requires additional diagnostic testing or medical/surgical intervention, and/or
- Test result leads to a change in study dosing or discontinuation from the study, significant additional concomitant drug treatment, or other therapy, and/or
- Test result is considered to be an adverse event by the investigator or sponsor.

Merely repeating an abnormal test, in the absence of any of the above conditions, does not constitute an AE. Any abnormal test result that is determined to be an error does not require reporting as an AE.

A **serious adverse event** (SAE) is any untoward medical occurrence at any dose that:

- Results in death.
- Is life-threatening as it occurred, i.e, the patient was at risk of death at the time of the event. This does not refer to an event which hypothetically might have caused death if it were more severe.
- Requires inpatient hospitalisation or prolongation of existing hospitalisation (see below for circumstances that do not constitute adverse events) .
- Results in persistent or significant disability/incapacity, defined as a substantial disruption of a patient's ability to conduct normal life functions.
- Results in a congenital anomaly or birth defect.
- Constitutes an important medical event, i.e, based upon appropriate medical judgement, event may jeopardise the patient and may require medical or surgical intervention to prevent one of the outcomes listed above.

HOSPITALIZATION

AEs reported from studies associated with hospitalization or prolongation of hospitalization are considered serious. Any initial admission (even if less than 24 hours) to a healthcare facility meets these criteria. Admission also includes transfer within the hospital to an acute/intensive care unit (e.g., from the psychiatric wing to a medical floor, medical floor to a coronary care unit, neurological floor to a tuberculosis unit). An emergency room visit does not necessarily constitute a hospitalization; however, an event leading to an emergency room visit should be assessed for medical importance.

Hospitalization in the absence of a medical AE is not in itself an AE and is not reportable. For example, the following reports of hospitalization without a medical AE are not to be reported.

- Social admission (e.g., patient has no place to sleep)
- Administrative admission (e.g., for yearly exam)
- Optional admission not associated with a precipitating medical AE (e.g., for elective cosmetic surgery)
- Hospitalization for observation without a medical AE
- Admission for treatment of a pre-existing condition not associated with the development of a new AE or with a worsening of the pre-existing condition (e.g., for work-up of persistent pre-treatment lab abnormality)
- Protocol-specified admission during clinical study (e.g., for a procedure required by the study protocol)

If there is any doubt about whether the information constitutes an AE, the information will be treated as an AE. Medical and scientific judgment is exercised in determining whether an event is an important medical event. An important medical event may not be immediately life-threatening and/or result in death or hospitalization. However, if it is determined that the event may jeopardize the patient or may require intervention to prevent one of the other adverse event outcomes, the important medical event should be reported as serious.

Examples of such events are intensive treatment in an emergency room or at home for allergic bronchospasm; blood dyscrasias or convulsions that do not result in hospitalization; or development of drug dependency or drug abuse.

CAUSALITY ASSESSMENT

The investigator's assessment of causality must be provided for all AEs (serious and non-serious). The investigator must record the causal relationship in the CRF, as appropriate, and

report such an assessment in accordance with the serious adverse reporting requirements if applicable.

An investigator's causality assessment is the determination of whether there exists a reasonable possibility that etanercept caused or contributed to an adverse event. If the investigator's final determination of causality is unknown and the investigator does not know whether etanercept caused the event, then the event will be handled as related to etanercept for reporting purposes. If the investigator's causality assessment is unknown but not related to etanercept this should be clearly documented in the CRF.

Scenarios necessitating reporting to Pfizer Safety within 24 hours

Scenarios involving exposure during pregnancy, exposure during breastfeeding, medication error, overdose, misuse, lack of efficacy, and occupational exposure are described below.

EXPOSURE DURING PREGNANCY

An exposure during pregnancy (EDP) occurs if:

1. A female becomes, or is found to be, pregnant either while receiving or having been directly exposed to (e.g., environmental exposure) etanercept, or the female becomes, or is found to be, pregnant after discontinuing and/or being directly exposed to etanercept (maternal exposure).
2. A male has been exposed, either due to treatment or environmental, to etanercept prior to or around the time of conception and/or is exposed during his partner's pregnancy (paternal exposure).

As a general rule, prospective and retrospective exposure during pregnancy reports from any source is reportable irrespective of the presence of an associated AE and the procedures for SAE reporting should be followed.

If any study patient or study patient's partner becomes, or is found to be, pregnant during the study patient's treatment with etanercept, the investigator must submit this information to Pfizer within 24 hours of awareness of the pregnancy, irrespective of whether an adverse event has occurred, using the NIS AEM Report Form and the EDP Supplemental Form.

Information submitted should include the anticipated date of delivery (see below for information related to termination of pregnancy).

Follow-up is conducted to obtain general information on the pregnancy; in addition, follow-up is conducted to obtain pregnancy outcome information on all EDP reports with an unknown outcome. The investigator will follow the pregnancy until completion or until pregnancy termination (e.g., induced abortion) and then notify Pfizer of the outcome. The

investigator will provide this information as a follow up to the initial EDP report. In the case of a live birth, the structural integrity of the neonate can be assessed at the time of birth. In the event of a termination, the reason(s) for termination should be specified and, if clinically possible, the structural integrity of the terminated fetus should be assessed by gross visual inspection (unless pre-procedure test findings are conclusive for a congenital anomaly and the findings are reported).

If the outcome of the pregnancy meets the criteria for an SAE (e.g., ectopic pregnancy, spontaneous abortion, intrauterine fetal demise, neonatal death, or congenital anomaly [in a live born, a terminated fetus, an intrauterine fetal demise, or a neonatal death]), the procedures for reporting SAEs should be followed.

Additional information about pregnancy outcomes that are reported as SAEs follows:

- Spontaneous abortion includes miscarriage and missed abortion;
- Neonatal deaths that occur within 1 month of birth should be reported, without regard to causality, as SAEs. In addition, infant deaths after 1 month should be reported as SAEs when the investigator assesses the infant death as related or possibly related to exposure to investigational product

Additional information regarding the exposure during pregnancy may be requested. Further follow-up of birth outcomes will be handled on a case-by-case basis (e.g., follow-up on preterm infants to identify developmental delays).

In the case of paternal exposure, the study participant will be provided with the Pregnant Partner Release of Information Form to deliver to his partner. It must be documented that the study participant was given this letter to provide to his partner

EXPOSURE DURING BREASTFEEDING

Scenarios of exposure during breastfeeding must be reported to Pfizer within 24 hours of awareness, irrespective of the presence of an associated AE.

MEDICATION ERROR

A medication error is any preventable event that may cause or lead to inappropriate medication use or patient harm while the medication is in the control of the health care professional, patient, or consumer. Such events may be related to professional practice, health care products, procedures, and systems including: prescribing; order communication; product labelling, packaging, and nomenclature; compounding; dispensing; distribution; administration; education; monitoring; and use.

Medication errors include:

- Near misses, involving or not involving a patient directly (e.g., inadvertent/erroneous administration, which is the accidental use of a product outside of labeling or prescription on the part of the healthcare provider or the patient/consumer)
- Confusion with regard to invented name (e.g., trade name, brand name)

The investigator must submit the following medication errors to Pfizer within 24 hours of awareness, irrespective of whether an adverse event occurred:

- Medication errors involving patient exposure to the product, whether or not the medication error is accompanied by an AE
- Medication errors including potential medication errors or near misses that do not involve a patient directly. When a medication error does not involve patient exposure to the product the following minimum criteria constitute a medication error report
 - An identifiable reporter
 - A suspect product
 - A medication error including potential medication error or near miss

LACK OF EFFICACY

Reports of lack of efficacy to etanercept are to be submitted to Pfizer by the investigator within 24 hours of awareness, irrespective of the presence of an associated AE/SAE or the indication for use of etanercept.

OVERDOSE AND MISUSE

The investigator must submit reports of overdose and misuse associated with the use of etanercept to Pfizer within 24 hours of awareness, irrespective of the presence of an associated AE/SAE.

OCCUPATIONAL EXPOSURE

Reports of occupational exposure to etanercept are to be submitted to Pfizer by the investigator within 24 hours of awareness, irrespective of the presence of an associated AE/SAE.

9.2. Adverse Event and Serious Adverse Event Recording and Reporting

Complete training on AE and SAE reporting practices will be provided to each participating site. Any AE/SAE observed by or reported to site personnel by the patient that occurs from the time of enrolment through patient discontinuation from the registry, end of the

observation period, or 28 days after last dose of etanercept, whichever is later, is potentially reportable. The RP must instruct the patient to report AEs (including SAEs, AEs of special interest and non-serious AEs)(see list under [Section 9.1](#)) during this time period.

Each AE is to be assessed to determine if it meets serious criteria. If a SAE occurs, expedited reporting will follow local and international regulations, as appropriate.

Medical and scientific judgment is exercised in determining whether an event is an important medical event. An important medical event may not be immediately life-threatening and/or result in death or hospitalization. However, if it is determined that the event may jeopardize the patient or may require intervention to prevent one of the other outcomes listed in the definition of SAE, the important medical event should be reported as serious.

Examples of such events are intensive treatment in an emergency room or at home for allergic bronchospasm, blood dyscrasias or convulsions that do not result in hospitalization, or development of drug dependency or drug abuse.

This study protocol may require review of the patient medical chart. Review of patient medical charts for specific attribution of SAEs to Pfizer drugs will not be actively pursued. However, while the primary purpose of this study does not encompass assessment of drug-related effects in individuals, the reviewer may identify an SAE with explicit attribution to a Pfizer drug via patient chart (and with an identifiable reporter). Such SAEs must be reported to Pfizer or its representative for submission to regulatory authorities. Explicit attribution is not inferred by a temporal relationship between drug administration and an SAE but must be based on a definite statement of causality by a healthcare provider linking drug administration to the SAE.

If there is a written notation in the medical chart indicating that a physician attributed a serious or non-serious adverse event to a Pfizer drug, Pfizer or its representative/the reviewer will record the event on the CRF, and report SAEs and non-serious AEs of interest, within 24 hours of awareness, to Pfizer Safety using the NIS AEM Report Form.

Scenarios involving drug exposure, including exposure during pregnancy, exposure during breast feeding, medication error, overdose, misuse, lack of efficacy and occupational exposure associated with the use of a Pfizer product must be reported, within 24 hours of awareness, to Pfizer Safety using the NIS AEM Report Form.

For these safety events with an explicit attribution to or associated with use of, respectively, a Pfizer product, the data captured in the medical record will constitute all clinical information known regarding these adverse events. No follow-up on related adverse events will be conducted.

SERIOUS ADVERSE EVENT REPORTING REQUIREMENTS

If a SAE occurs, Pfizer is to be notified within 24 hours of awareness of the event by the investigator. In particular, if the SAE is fatal or life-threatening, notification to Pfizer must be made immediately, irrespective of the extent of available AE information. This timeframe also applies to additional new information (follow-up) on previously forwarded SAE reports as well as to the initial and follow-up reporting of exposure during pregnancy, exposure during breast feeding and medication error cases.

In the rare event that the investigator does not become aware of the occurrence of a SAE immediately (e.g., if an outpatient study patient initially seeks treatment elsewhere), the investigator is to report the event within 24 hours after learning of it and document the time of his/her first awareness of the SAE.

For all SAEs, the investigator is obligated to pursue and provide information to Pfizer in accordance with the timeframes for reporting specified above. In addition, an investigator may be requested by Pfizer to obtain specific additional follow-up information in an expedited fashion. This information collected for SAEs is more detailed than that captured on the AE CRF. In general, this will include a description of the AE in sufficient detail to allow for a complete medical assessment of the case and independent determination of possible causality. Information on other possible causes of the event, such as concomitant medications and illnesses must be provided. In the case of a patient death, a summary of available autopsy findings must be submitted as soon as possible to Pfizer or its designated representative.

The CRO EDC System will include a AE/SAE CRF for site staff to record basic information for any reportable AEs noted by the site or reported to the site by the patient. Entry of the CRF will generate an automated notification to CRO's registry staff to ensure appropriate follow up.

Recording of AEs/SAEs on the CRF does not satisfy the requirements for expedited reporting of events for regulatory reporting purposes.

The site is also required to fax a completed Non-Interventional Study (NIS) AEM Report Form to CRO each time a SAE or an AE of interest is reported. The document will then be transmitted to Pfizer's Drug Safety Unit within 24 hours for further processing and evaluation.

In case a pregnancy should be reported, site will complete a NIS AEM Report Form as well as the EDP Supplemental Form. Upon receipt of an automated email notification, if follow-up required, the CRO will immediately contact the site and request that the required Form(s) containing the minimum information (reportable event, identifiable subject, identifiable reporter and exposure to etanercept), is faxed to the CRO without delay. Upon receipt of the Form(s), the CRO immediately faxes it (them) to Pfizer local Drug Safety Unit (DSU), even

if minimal information is missing. The CRO then forwards the information to the Medical Monitor at the CRO via email.

All SAEs, pregnancies and AEs of interest (as listed under [Section 9.1](#)), and follow-up information must be reported within 24 hours by faxing a completed NIS AEM Report Form to the study center at CRO and confirming by phone or e-mail that the fax was received.

Additionally to the NIS AEM Report Form, pregnancy should also be reported using the EDP Supplemental Form.

All NIS AEM Report Forms and EDP Supplemental Forms should be faxed to the study center at CRO.

In order to maintain compliance with the EMA and other international regulatory bodies, sites may be further contacted by the registry staff or Pfizer safety personnel in order to collect additional information required to evaluate a potential SAE.

It is the responsibility of the site to inform their IEC (or equivalent local body governing research) of relevant SAEs occurring at their site, according to local requirements. Pfizer or CRO will notify the sites of any emergent product-related safety issues in accordance with local requirements.

COMMUNICATION OF ISSUES

In the event of any prohibition or restriction imposed (e.g., clinical hold) by an applicable Competent Authority in any area of the world, or if the investigator is aware of any new information which might influence the evaluation of the benefits and risks of etanercept, Pfizer should be informed immediately.

In addition, the investigator will inform Pfizer immediately of any urgent safety measures taken by the investigator to protect the study patients against any immediate hazard, and of any serious breaches of this NI study protocol that the investigator becomes aware of.

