2. STUDY OBJECTIVES AND ENDPOINTS

The objectives of this study are to:

- Describe the risk of serious and pre-specified opportunistic infections (including tuberculosis) associated with current or recent treatment with etanercept in paediatric plaque psoriasis;

- Describe the long-term risk of incident malignancy in paediatric plaque psoriasis patients who have ever received etanercept;
- Identify any new, serious potentially unrecognised adverse drug reactions (ADRs) by collecting serious adverse event data in this population; and
- Assess effectiveness by describing patterns of treatment with etanercept, including premature discontinuation of etanercept and subsequent treatment with systemic therapies (including re-treatment with etanercept).

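### Protocol 9.2 rules out follow-up of chart-identified events attributed to a Pfizer product, with no exception for etanercept, and so contradicts the follow-up duties in Sections 9, 9.1 and 9.2 itself

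*Protocol*

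**What the plan says.** Protocol 9.2 contains a block on events found by reviewing patient charts. Charts will not be searched for attributions to the sponsor's drugs, but an SAE that a reviewer finds with an explicit attribution must be reported. On what counts as explicit, the text says: "Explicit attribution is not inferred by a temporal relationship between drug administration and an SAE but must be based on a definite statement of causality". A companion paragraph begins "If there is a written notation in the medical chart indicating that a physician attributed a serious or non-serious adverse event to a Pfizer drug" and then requires the event to be entered on the CRF, with SAEs and non-serious events of interest reported within 24 hours. Next comes a paragraph on special scenarios (pregnancy and breastfeeding exposure, medication error, overdose, misuse, lack of efficacy, occupational exposure), which must also be reported within 24 hours. The block closes by treating the chart as the whole of the clinical information on these events and stating: "No follow-up on related adverse events will be conducted".

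Other parts of the protocol read differently:

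- Section 9, on recording: "All observed or volunteered adverse events regardless of treatment group (if applicable) or suspected causal relationship to etanercept will be recorded".
- Section 9, on follow-up: "For adverse events with a causal relationship to etanercept, follow-up by the investigator is required until the event or its sequels resolve or stabilize".
- Section 9, on patients seen or hospitalised elsewhere: the site must do all it can to obtain the details from the outside provider.
- Section 9.1, Exposure During Pregnancy: the investigator follows the pregnancy to its end and reports the outcome.
- Section 9.2, Serious Adverse Event Reporting Requirements: "For all SAEs, the investigator is obligated to pursue and provide information to Pfizer in accordance with the timeframes for reporting specified above".
- Section 6.2.1: SAEs before enrolment are abstracted from records, all of them, and analysed separately.

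The third objective in Section 2 is: "Identify any new, serious potentially unrecognised adverse drug reactions (ADRs) by collecting serious adverse event data in this population".

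**The concern.** The events for which 9.2 rules out follow-up include those that Section 9 singles out for it: events a physician has linked to the drug. The registry concerns one Pfizer product, etanercept, and nothing in the chart-review block exempts that product or the enrolled patients.

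The block is not confined to a source outside the plan. Charts are a planned safety source. Section 2.1.1 has the registry physician review records to confirm events and obtain other providers' records where needed. Section 6.2 provides for retrieving records from other care settings and for abstracting safety information for patients already on etanercept. Section 6.2.1 relies on the events of interest being documented in the physician's chart.

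At stake is uniform handling. Two sites following the same protocol could treat the same hospitalisation differently, depending on which paragraph they applied. The attribution trigger adds a second problem. A reaction already attributed in writing has been recognised by someone, so an attribution rule is a poor guide for a route that should also pick up unrecognised ones.

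**Working it through.** No figure is involved, so the check sets the passages side by side and applies them to four cases.

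| Case | Chart-review text in 9.2 | Other text | Result |
|---|---|---|---|
| A. After enrolment, a hospital letter attributes an SAE to etanercept | Record and report; no follow-up | Section 9: follow related events to resolution or stabilisation, and pursue details from outside providers. 9.2 SAE requirements: pursue information on all SAEs | Direct contradiction |
| B. Pregnancy exposure to etanercept noted in a chart | Report within 24 hours; falls under the closing no-follow-up sentence | 9.1: follow to pregnancy outcome. 9.2 SAE requirements: a time limit for follow-up reports on pregnancy exposure | Direct contradiction |
| C. After enrolment, a hospital letter describes an SAE and is silent on cause | No stated duty; the trigger is a written attribution | Section 9: record whatever the suspected cause. 9.2 SAE requirements: report within 24 hours of learning of an SAE treated elsewhere | Poor fit; no express exemption, but a site could infer one |
| D. SAE before enrolment, found on abstraction, no attribution | No stated duty | 6.2.1: collect all retrospective SAEs | Poor fit, with 6.2.1 only; the Section 9 reporting period starts at enrolment |

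**Cases A and B.** One text says follow-up happens and the other says it does not. No order of precedence is given.

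**Case C.** The wrong inference is easy to draw. The Section 9 reporting period speaks of events that site staff observe or that the patient or caregiver reports, and 9.2 opens in similar terms. A site could conclude that an event known only from a chart lies outside that language and is governed solely by the chart-review block, where reporting "must be based on a definite statement of causality by a healthcare provider linking drug administration to the SAE".

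**Reach.** Interviews every 3 months in years 1 and 2 and every 6 months afterwards ask open and outcome-specific questions, and anything observed or volunteered is recorded whatever the cause. Cases C and D therefore matter only for events that surface through the chart alone. Neither document gives the share of events first learned of in that way, nor the share of those without a written attribution.

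**The case against.** The best defence is that the chart-review block has a narrower purpose. Its actor is the sponsor, its representative or a chart reviewer, and its subject is any Pfizer drug. The Section 9 follow-up rule and the 9.2 SAE rule bind the investigator, and the former concerns etanercept. On that reading the block deals with incidental findings by a reviewer and leaves the investigator's duties untouched. The reading is reasonable, but the protocol does not state that scope, and even if it did, the closing sentence would still clash with the pregnancy follow-up in 9.1 and the duty on all SAEs in 9.2.

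Several other objections stand, and they limit the point:

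- A reader might infer that only attributed events are reportable. The text says attributed events must be reported; it does not exempt the others, and the special scenarios need no causality statement.
- A reader might infer that 9.2 disowns the registry's safety purpose, since it says the primary purpose does not cover assessing drug-related effects. That sentence is limited to effects in individuals, whereas the third objective works through SAE data in the population.
- A reader might infer that endpoint data will be missing. Separate provisions seek those data: record review and outside records in Protocol 2.1.1, pathology or histology for malignancy in 2.1.1.2, and supporting information and safety follow-up reports in SAP 5.1.
- Pre-enrolment SAEs are already collected in full under 6.2.1, and Section 7.1 limits the primary analyses to prospective data.

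**Conclusion.** Wrong as written: an internal contradiction over follow-up. As it stands, 9.2 stops follow-up of chart-identified events attributed to or associated with etanercept, while Sections 9, 9.1 and another part of 9.2 require it. This conclusion rests on the wording alone and needs no assumption about event rates.

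The attribution trigger is a lesser, secondary problem. It could lead sites to leave unreported an unattributed event known only from a chart, which weakens capture for the third objective. It would go too far to say that the unrecognised reactions are filtered out: observed, volunteered and interview-elicited events are recorded regardless of cause, and SAEs treated elsewhere must be reported once the investigator learns of them. No size can be given, because the documents hold no figure from which to derive one.

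**What to change.** Reconcile Protocol 6.2.1, 9, 9.1 and 9.2 as follows:

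1. Add a scope sentence to 9.2 limiting the chart-review, explicit-attribution and no-follow-up text to Pfizer products other than etanercept.
2. State that any AE or SAE in an enrolled patient during the reporting period, including one learned of from records, falls under the Section 9 rules on recording, causality and follow-up.
3. State that SAEs before enrolment are collected regardless of attribution, as 6.2.1 already provides.
4. Keep the paragraph requiring the special scenarios to be reported within 24 hours.

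A scope sentence is better than deleting the block. Deletion back from the no-follow-up sentence would also remove the scenario paragraph and the rule for events attributed to the sponsor's other products.

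The cost is protocol wording and a site training note. The downside is a few more SAE forms and queries for events found in charts.
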